6.3 Follow-up Period

6.3.1 Safety Follow-up Visits (Interim 8-week and Final 16-week)

All subjects will be followed for 16 weeks after the last dose of IP or until the Final Safety Follow-up Visit, whichever is longer, for AE reporting, as well as SAEs made known to the Investigator at any time thereafter that are suspected of being related to IP, as described in Section [10.2.3](#).

In the Induction Phase, subjects who discontinue from the study prior to completing Week 24, or subjects who complete Week 24 and do not enter the Maintenance Phase or the OLE study will return for an Interim and a Final Safety Follow-up Visit at 8 and 16 weeks, respectively after final IP administration (at Week 31 and Week 39 for subjects completing the Induction Phase) for the assessment of safety and clinical status after exiting the study. However, subjects who are permanently discontinued from IP and continue study participation in order to complete safety and efficacy assessments in the phase of the study that permanent discontinuation from IP occurs (according to Section [11.1](#)) will return for the Interim and Final Safety Follow-up Visits 8 and 16 weeks after their last study visit instead of their last dose of IP (eg, Week 24 or the ET Visit). Assessments should be performed in accordance with the Table of Events ([Table 4](#)). Subjects who

* Note that EGD is not required for ET Visits occurring before Week 8 in the Induction Phase or before Week 32 in the Maintenance Phase.

continue participation in the Maintenance Phase or OLE study will not return for the 2 Safety Follow-up Visits.

In the Maintenance Phase, subjects who discontinue from the study prior to completing Week 48 or complete Week 48 but do not enroll in the OLE study will also return for an Interim and a Final Safety Follow-up Visit at 8 and 16 weeks, respectively after final IP administration (at Week 55 and Week 63 for completers of the Maintenance Phase) for the assessment of safety and clinical status after exiting the study. However, subjects who are permanently discontinued from IP and continue study participation in order to complete safety and efficacy assessments in the phase of the study that permanent discontinuation from IP occurs (according to Section 11.1) will return for the Interim and Final Safety Follow-up Visits 8 and 16 weeks after their last study visit instead of their last dose of IP (eg, Week 48 or the ET Visit). Assessments to be performed are presented in the Table of Events (Table 5). Subjects who continue participation in the OLE study will not return for the 2 Safety Follow-up Visits.

The following evaluations will be performed as specified in Table 4 and Table 5:

- Concomitant therapy
- Assessment of AEs/SAEs (monitored through 16 weeks after the last dose of IP or the Final Safety Follow-up Visit, whichever is longer)
- Hematology, chemistry, and urinalysis
- Pregnancy test (only for FCBP)
- Physical examination
- Weight
- Vital signs
- Serum antibodies to CC-93538
- Serum CC-93538 PK assessment

[REDACTED]

- Modified Daily Symptom Diary (mDSD) only for the 14-day period preceding each of the 2 Safety Follow-up Visits
- Phone call reminder for mDSD completion just prior to the 14-day collection period preceding each of the 2 Safety Follow-up Visits

[REDACTED]

6.4 Efficacy Assessment

6.4.1 *Esophagogastroduodenoscopy (EGD)*

To ensure quality data and standardization, the same person should perform endoscopic procedures at a study site at each study visit.

The EGD biopsy results for eosinophil counts will be read blinded to treatment allocation at a centralized reading facility. Biopsy specimens will be sent to the centralized reading facility, and with the exception of screening, results of the centrally read eosinophil counts will be blinded to

investigative sites. After randomization, a local histologic assessment of EGD biopsy samples should not be performed, unless required for safety reasons (eg, severe EoE flare, AEs, or incidental findings, etc.). Any incidental findings of potential clinical relevance that are not directly associated with the objectives of the study should be evaluated and handled by the Investigator per the site's standard of care and clinical judgement. More detailed instructions for specimen processing, storage, and shipping will be provided in a separate Study Laboratory Manual.

Endoscopic procedures will be performed as follows:

- EGD will be performed at the time points specified in the Table of Events ([Table 4](#) and [Table 5](#)).
- Biopsies should be obtained from 3 levels, the proximal, mid, and distal esophagus, to maximize the likelihood of meeting histologic eligibility criteria for this study as follows:
 - Distal esophagus (3 to 5 cm above the Z-line [squamo-columnar junction])
 - Proximal esophagus (\approx 15 cm above the Z-line and within 10 cm of the esophageal inlet)
 - Mid esophagus (dependent on subject anatomy as described in the Study Laboratory Manual)
- All subsequent biopsies should be obtained from the same levels as the screening biopsies (ie, all 3 levels) maintaining consistency throughout the study.
- Biopsy samples must be obtained from 2 to 4 separate areas at each level, ideally from the areas with the most prominent visible abnormalities. For example, if 2-bite biopsies are being obtained, a minimum total of 4 biopsy fragments (from 2 separate 2-bite biopsies) would be obtained from each esophageal level.
- The screening EGD must be performed within 8 weeks prior to Day 1. The Investigator must document all treatments received at the time of the EGD and biopsy (for any indication) through Day 1, and the subject must not have received any new treatment that might affect EoE since the time of EGD according to protocol requirements (see Section 8). Subjects should not undergo the screening EGD during the 14-day period just prior to baseline when the final 14 days of the screening mDSD is collected.
- Histologic analysis of the esophageal biopsy samples for any study-specific assessments will be performed by a central laboratory including enumeration of eosinophil count (peak eosinophil count) by analysis of hematoxylin and eosin (H&E) stained biopsies and EoE histology scoring system (EoEHSS) assessment (histology grade and stage score).
- Endoscopic findings will be assessed by each Investigator using the EoE EREFS ([Hirano, 2013](#)) in 5 classification categories at the time points specified in the Table of Events ([Table 4](#) and [Table 5](#)). The classification features include edema, fixed rings, exudates, furrows, and stricture. Assessments will be conducted at all 3 levels of the esophagus (the proximal, mid, and distal).
- In addition to obtaining the eosinophil counts required for inclusion in the study and primary endpoint determination, the esophageal biopsies will be used for evaluation of potential diagnostic [REDACTED] using appropriate laboratory methodology, including histopathology, immunohistochemistry, and transcript profiling.

6.4.2 Clinical Symptoms of EoE

6.4.2.1 Modified Daily Symptom Diary (mDSD)

The mDSD is a patient-reported diary to assess the daily experience of dysphagia symptoms ([APPENDIX B](#)). The original 4-item version of the DSD utilized in Phase 2 was modified to reflect the findings from the concept elicitation and cognitive interviews conducted with adolescent and adult EoE subjects in the mDSD validation study, EVA-20655. The mDSD includes 6 primary questions and 2 sub-questions, including an assessment of solid food consumption that day (item 1), experience with trouble swallowing (item 2), food going down slowly (item 3), food getting stuck in the throat or chest (item 4), actions taken by subjects to obtain relief (item 5), and any pain associated with swallowing (item 6). The recall period is “today,” as the diary is meant to be completed daily.

[figure not shown]
The mDSD questions 2, 3, and 4 represent the primary symptoms to determine if a subject is experiencing dysphagia on any given day. Specifically, a DD is defined as a “yes” response to any or all of mDSD questions 2, 3, and 4. The mDSD composite score utilizes participant responses to mDSD questions 2, 3, 4, and 5. Subjects will receive a single score of “1” for any or all “yes” response(s) to questions 2, 3, or 4 in order to capture an episode of dysphagia experienced during the day and will receive a score of 0 to 4 for the response to question 5 depending on the action taken to seek relief for the dysphagia episode. Scores range from 0 to 70, with higher scores indicating more frequent and/or severe dysphagia.

[figure not shown]
Subjects will complete the mDSD daily via an eDiary on a handheld device for at least the last 3 consecutive weeks during the Screening Period. Subjects are required to have completed at least 11 days of mDSD data collection out of the final 14 days of screening (ie, the final 14-day period preceding Day 1) in order to be enrolled in the study. A number of measures will be employed in order to enhance subject adherence to eDairy completion and limit the amount of missing data, which is critical to ensure interpretability of mDSD assessment in this study. First, eDiary reminder alarms will allow subjects to select the timing for their alarm within a standardized window every evening such that completion occurs after the subject’s last meal of the day. Second, ongoing surveillance of diary completion data will occur in order to correct any issues as close to real time as possible. Third, subjects will receive reminder calls from site staff in advance of the 14-day collection period preceding the screening (baseline) assessment and the Week 24 and 48 assessments (as well as additional times as needed based on ongoing surveillance) to help ensure compliance with the daily diary completion requirements at critical assessment points during the study. In addition, for subjects who are required to complete the Safety Follow-up Visits ([Section 6.3.1](#)), a phone contact will be made ahead of the 14-day period before each of the 2 Safety Follow-up Visits.

The mDSD will be administered daily in the evening or at bedtime after the subject’s last meal of the day via an eDiary for at least the last 3 consecutive weeks (at least 21 days, but up to 28 days) in screening, from Day 1 through Week 48 (through the duration of the Induction and Maintenance Phases) of the study, through the ET Visit (if applicable), and for the 14-day period just prior to each of the 2 Safety Follow-up Visits (if applicable) according to the Table of Events ([Table 4](#) and

Table 5). Subjects are instructed to continue daily completion of the mDSD in the time interval between the transition from Induction Phase to Maintenance Phase or Study CC-93538-EE-001 to the OLE study.

Further assessment of the psychometric properties of the mDSD in a Phase 3 study will include a preliminary blinded analysis after the first one-third of subjects complete 24 weeks of treatment in the Induction Phase as well as a final analysis, in all subjects completing Week 24, at the end of the study. These analyses will focus on the reproducibility, validity, and responsiveness of the DD and mDSD composite score endpoints as well as confirmation of the clinically meaningful response definition for the clinical co-primary endpoint, mean change in DD from baseline to Week 24, as described in a separate Psychometric Analysis Plan. The reproducibility of the mDSD will be assessed among “stable” subjects (ie, those reporting no change in [REDACTED] rating at Week 2) using 2 consecutive 14-day periods, the final 14-days of screening (baseline) and Weeks 1 to 2.

6.4.2.7 *Worsening of EoE Symptoms, EoE Flare, and the EoE Flare Assessment Visit*

Subjects with a worsening of EoE symptoms during the study, either in the Induction Phase or Maintenance Phase will be required to complete the EoE Flare Assessment Visit as shown in the Table of Events ([Table 4](#) and [Table 5](#)). Subjects with increased signs and symptoms of EoE are instructed to contact the Investigator and/or study staff to determine if an EoE Flare Assessment Visit is warranted.

An EoE Flare Assessment Visit including safety and efficacy evaluations can occur at any time during the study. An EGD is required at EoE Flare Assessment Visits to determine if use of rescue therapy is clinically indicated. Alternatively, if endoscopy is conducted as an intervention during an emergency department visit or hospitalization for a worsening of EoE symptoms or flare, medical record source data including details of the endoscopic procedure should be collected for the EoE Flare Assessment Visit EGD requirement. In addition, all attempts should be made to collect biopsy samples, and these samples should be sent to the central reader for histologic analysis.

The Investigator will confirm if the worsening of EoE symptoms requires rescue therapy and, thus, is deemed a severe EoE flare according to the following protocol definitions.

Any worsening of EoE symptoms during study participation will be documented as an EoE flare.

- A severe EoE flare is defined as any worsening of EoE symptoms including a high intensity episode resulting in emergency department visit or hospitalization, with the need for endoscopic intervention (eg, for prolonged food impaction) and/or need for rescue therapy (eg, including but not limited to corticosteroid therapy or dilation), or a worsening of EoE symptoms resulting in the need for rescue therapy only without endoscopic intervention.
- A mild to moderate EoE flare is defined as any worsening of EoE symptoms without the need for rescue therapy or endoscopic intervention.

ET procedures performed at the EoE Flare Assessment Visit do not need to be repeated for subjects who discontinue the study prematurely due to an EoE flare.

Induction Phase

In the Induction Phase, if a subject experiences a severe EoE flare requiring intervention with endoscopy and/or treatment with any rescue therapy (eg, including but not limited to systemic or swallowed topical corticosteroid therapy or dilation), the subject may continue participation in the Induction Phase with concomitant rescue therapy as needed until completion of the Induction Phase at Week 24. The subject will not meet the entry criteria for the Maintenance Phase. The subject will be eligible to enroll in the OLE Study, CC-93538-EE-002, based on the judgement of the Investigator after completing Week 24 of the Induction Phase.

Subjects participating in the Induction Phase who require pharmacotherapy or dietary modifications prohibited by the protocol that may affect CC-93538 efficacy assessment or a dilation procedure will not be eligible for entry into the Maintenance Phase. Refer to Maintenance entry criteria in Section [6.4.2.8](#).

Maintenance Phase

In the Maintenance Phase, if a subject experiences a severe EoE flare requiring intervention with endoscopy and/or treatment with any rescue therapy (eg, including but not limited to systemic or swallowed topical corticosteroid therapy or dilation), the subject may continue participation in the Maintenance Phase with concomitant rescue therapy as needed until completion of the Maintenance Phase at Week 48. The subject will be eligible to enroll in the OLE Study, CC-93538-EE-002, based on the judgement of the Investigator after completing the study (Week 48).

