^b The Day 1 assessments will serve as baseline measurements and will be conducted before dose administration.

^c For subjects continuing in the Maintenance Phase, Visit 8 (Week 24) of the Induction Phase will also be the first visit in the Maintenance Phase. See [Table 5](#) for the Table of Events for the Maintenance Phase.

^d In the event of scheduling challenges, EGD may be performed with a +7 days visit window. All assessments are to be performed prior to IP administration for the first day of dosing in the Maintenance Phase.

^e An EoE Flare Assessment Visit should be scheduled as close as possible to the time that an EoE flare is suspected. Note that laboratory samples do not need to be a pre-dose draw unless the subject is expected to dose later that day.

^f Subjects who discontinue the study prior to completing the 24-week Induction Phase will be asked to complete an ET Visit and an Interim and a Final Safety Follow-up Visit at 8 weeks and at 16 weeks, respectively, after final IP administration for the assessment of safety and clinical status. Early Termination procedures performed at the EoE Flare Assessment Visit do not need to be repeated for subjects discontinuing the study prematurely due to an EoE flare.

[figure not shown]
^g Subjects who complete the Induction Phase and do not enter either the Maintenance Phase or OLE study will be asked to complete the Interim 8-week Safety Follow-up Visit (8 weeks after final IP administration; at Week 31 for subjects that complete the Induction Phase) and the Final 16-week Safety Follow-up Visit (16 weeks after final IP administration; at Week 39 for subjects that complete the Induction Phase) for the assessment of safety and clinical status. For subjects exiting the study before completing the Induction Phase, these visits should occur at 8 and 16 weeks following the last dose of IP (ie, visits may occur before Week 31 and 39). However, subjects who are permanently discontinued from IP and continue study participation will return for the Interim and Final Safety Follow-up Visits 8 and 16 weeks after their last study visit instead of their last dose of IP (eg, Week 24 or the ET Visit).

^h Pre-dose collection, except for Safety Follow-up Visits (if applicable), the ET Visit (if applicable), and the EoE Flare Assessment Visit (if applicable; unless dose is taken that day).

[figure not shown]

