ⁱ Fasting Lipid Panel and fasting glucose (instead of random glucose) will only be conducted at Day 1, Week 24, and the ET Visit (if applicable).

^j For females of childbearing potential (FCBP), a serum pregnancy test at screening, urine (or serum) pregnancy test at Day 1, and urine pregnancy tests at subsequent visits are required. In the event of a positive urine test, the subject is not to be dosed, and confirmation with a serum pregnancy test should be performed. At each study visit, the Investigator will counsel FCBP subjects on pregnancy precautions for the duration of the study. Additional pregnancy tests may be required per local guidelines.

^k Complete physical examination will be conducted at screening, Day 1, Week 24, both Safety Follow-up Visits (if applicable), and at the ET Visit (if applicable). Abbreviated physical examination will be conducted at Weeks 4, 8, 12, 16, and 20.

^m Serum will be collected at Day 1 (baseline), Week 24, and the ET Visit (if applicable) as well as approximately 4 weeks after a documented or suspected SARS-CoV-2 infection, for possible measurements of [REDACTED] per national and local requirements [REDACTED].

^o A phone call will be made to subjects as a reminder to complete the mDSD. The Table of Events X's are noted in the visit before the start of the collection period in order to alert sites to the upcoming interim visit activity. Phone calls will take place just prior to the beginning of the final 14-day mDSD data collection period for screening (just prior to Day -14) and for the Week 24 (just prior to Week 22) endpoint analyses. For subjects who are required to complete the Safety Follow-up Visits, a phone call will take place before the 14-day mDSD data collection period just prior to the Interim Safety Follow-up Visit and the Final Safety Follow-up Visit, if applicable. During this call, subjects will also be reminded to complete the [REDACTED] at Day -14.

^p The mDSD will be completed daily after the last meal of the day for at least the last 3 consecutive weeks (at least 21 days [up to 28 days]) during the Screening Period and daily from Day 1 through Week 24 using an electronic diary (eDiary) on a handheld device (ePRO instrument). For subjects who are required to complete the Safety Follow-up Visits, the mDSD will also be completed daily for the 14-day period before each of the 2 Safety Follow-up Visits. The ePRO

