- ^d Subjects who complete the Maintenance Phase and do not enter the OLE study will be asked to complete the Interim 8-week Safety Follow-up Visit (8 weeks after final IP administration; at Week 55 for subjects that complete the Maintenance Phase) and the Final 16-week Safety Follow-up Visit (16 weeks following final IP administration; at Week 63 for subjects that complete the Maintenance Phase) for assessment of safety and clinical status. For subjects exiting the study before completing the Maintenance Phase, these visits should occur at 8 and 16 weeks following the last dose of IP (ie, visits may occur before Week 55 and 63). However, subjects who are permanently discontinued from IP and continue study participation will return for the Interim and Final Safety Follow-up Visits 8 and 16 weeks after their last study visit instead of their last dose of IP (eg, Week 48 or the ET Visit).
- ^e Pre-dose collection except for Safety Follow-up Visits (if applicable), the ET Visit (if applicable), and the EoE Flare Visit (if applicable; unless a dose is taken that day).
- ^f Fasting Lipid Panel and fasting glucose (instead of random glucose) will only be conducted at Week 24, Week 48, and the ET Visit (if applicable).
- ^g For females of childbearing potential (FCBP), urine pregnancy tests are required. In the event of a positive urine test, the subject is not to be dosed, and confirmation with a serum pregnancy test should be performed. At each study visit, the Investigator will counsel FCBP subjects on pregnancy precautions for the duration of the study. Additional pregnancy test may be required per local guidelines.
- ^h Complete physical examination to be performed at Maintenance Phase Week 24, Week 48, both Safety Follow-up Visits (if applicable) and at the ET Visit (if applicable). Abbreviated physical examination to be conducted at Week 36.

[figure not shown]

- ^j Serum will be collected at Week 24, Week 48 and the ET Visit (if applicable) as well as approximately 4 weeks after a documented or suspected SARS-CoV-2 infection, for possible measurements of [REDACTED] per national and local requirements [REDACTED]

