	ICE 1: Treatment discontinuation in subjects without the use of concomitant rescue therapy or prohibited medication before the planned 24 weeks	Treatment Policy	Observations post ICE are used to reflect clinical practice
Population-level Summary	ICE 2: The use of concomitant rescue therapy or prohibited medication which may impact the efficacy assessment for CC-93538, regardless of treatment discontinuation, before the planned 24 weeks	Composite Variable	Data post ICE will be set as non-responders to reflect treatment failure
	Difference in proportions between treatment groups		

9.6.1.2 *Change in Dysphagia Days (DD) from Baseline to Week 24 (Induction Phase)*

The mean change in dysphagia days (DD), evaluated over the prior 14-day period using the mDSD, from baseline to Week 24 is one of the 2 co-primary endpoints for the Induction Phase.

A DD is defined as a “yes” response to any or all of mDSD questions 2, 3, and 4. In calculating the number of DD for each subject, if the number of measurable diary days (defined as a diary day for which Questions 2 to 4 are answered) over the 14-day period prior to Day 1 is less than 11 or post-Day 1 visits are less than 8, the normalization formula will not be applied and the value of DD will be set to missing. In addition, subjects with at least 8 measurable diary days at post-Day 1 visits that are very unbalanced across the two weeks, defined as less than 3 measurable diary days in either the first or second week, will also have the value of DD set to missing.

The primary analysis will be conducted on the ITT population based on an analysis of covariance (ANCOVA) model with treatment group, Steroid Inadequate Responders/Intolerant status (yes or no), and baseline DD values included in the model. The comparison between CC-93538 360 mg SC once weekly and placebo for change in DD from baseline at Week 24 will be made using the difference in least squares (LS) mean at a 5% 2-sided significance level. Point estimates for the mean difference between the 2 treatment groups using the adjusted LS Mean changes and corresponding 95% Wald CI will be reported. In addition, adjusted LS Means with standard error (SE), arithmetic means with standard deviation (SD), and arithmetic mean changes with SD will be summarized by treatment group.

Missing data will be handled using a multiple imputation (MI) approach ([SAS Institute, 2015](#)) under a missing at random (MAR) assumption.

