11.2 Study Discontinuation

The following events are considered sufficient reasons for discontinuing a subject from the study:

- Withdrawal by subject or parent/guardian
- Lost to follow-up
- Death
- Other (to be specified on the eCRF)

Note that subjects who are permanently discontinued from IP (as detailed in Section 11.1) but are not discontinued from the study will be encouraged to continue participation in order to complete all remaining required study assessments in the phase of the study that permanent discontinuation from IP occurs. In order to prevent missing data, the site staff will ensure attempts are made to reach subjects by phone or email that do not maintain contact with the Investigator.

The reason for study discontinuation should be recorded in the eCRF and in the source documents. Because follow-up of subjects who discontinue from the study prematurely is of particular importance, every attempt should be made to collect all or specific final data on a discontinued subject.

In the Induction Phase, subjects who discontinue from the study for any reason prior to completing Week 24, or who complete Week 24 and do not enter the Maintenance Phase will complete an ET

Visit conducted as close as possible to the time of study discontinuation. If study discontinuation occurs at the regularly scheduled visit (eg, Induction Phase Week 24) the ET Visit/procedures should be performed. These subjects, with the exception of those continuing in the OLE, will also have 2 Safety Follow-up Visits (at 8 and 16 weeks) after final IP administration for the assessment of safety and clinical status after exiting the study. For subjects who are permanently discontinued from IP during the Induction Phase and remain in the study to complete safety and efficacy assessments, the Interim and Final Safety Follow-up Visits will be conducted 8 and 16 weeks, respectively, after their last study visit in the Induction Phase. Assessments should be performed in accordance to the schedule of events ([Table 4](#)).

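### Subjects who leave the study early complete the diary mostly outside the 14 days that the Week 24 and Week 48 dysphagia-day endpoints use, even while still in safety follow-up

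*Combined protocol and SAP*

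**What the plan says.** **Diary.** Section 6.4.2.1 asks for the mDSD daily from Day 1 through Week 48. For a subject who leaves early it runs "through the ET Visit (if applicable), and for the 14-day period just prior to" each follow-up visit. Table 4 footnote p says the same: "the mDSD will also be completed daily for the 14-day period before each of the 2 Safety Follow-up Visits". Section 6.3.1 confirms that nothing more is collected in follow-up: "Modified Daily Symptom Diary (mDSD) only for the 14-day period preceding each of the 2 Safety Follow-up Visits".

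**Timing of follow-up visits.** For Induction leavers, Table 4 footnote g says "these visits should occur at 8 and 16 weeks following the last dose of IP". Table 5 footnote d gives the same rule for Maintenance: "For subjects exiting the study before completing the Maintenance Phase, these visits should occur at 8 and 16 weeks" after the last dose. There is one exception. Subjects who stopped treatment but continued participation are timed from their last study visit "instead of their last dose of IP (eg, Week 24 or the ET Visit").

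**Endpoint.** Section 9.6.1.2 evaluates DD over the 14 days before Week 24. A post-Day 1 value is set to missing with fewer than 8 measurable days, or fewer than 3 in either week. "Missing data will be handled using a multiple imputation (MI) approach" under a missing-at-random (MAR) assumption, with a tipping-point sensitivity analysis.

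**Subjects who stop treatment but stay.** Sections 11.1 and 11.2 encourage them to complete all remaining assessments of the phase, which includes the daily diary.

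**Leavers.** Section 11.2 opens its data-collection sentence with "Because follow-up of subjects who discontinue from the study prematurely is of particular importance" and asks for every attempt at final data. It names no diary window.

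**The concern.** The plan expects early leavers to return twice and to complete up to 28 more diary days with reminder calls. Nothing places those days where the co-primary endpoint needs them. A subject can therefore be in follow-up at Week 24, with a working diary device, and still have no evaluable Week 24 DD.

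At stake is how far the symptom co-primary depends on MAR imputation. Leavers stay in the ITT analysis, so every value not observed must be imputed. Off-treatment symptoms are the information that MAR imputation is least able to supply from subjects who stayed on treatment.

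**Working it through.** **1. Reproduce the plan's calendar.** Week w is Day 7w + 1. An Induction completer's last dose is at Week 23. Adding 8 and 16 weeks gives Week 31 (Day 218) and Week 39 (Day 274), as in Table 4. For Maintenance, the last dose at Week 47 gives Week 55 (Day 386) and Week 63 (Day 442), as in Table 5.

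**2. Set the windows against the endpoint.** Week 24 is Day 169, so the endpoint uses Days 155–161 (first week) and 162–168 (second week). For a last dose at Week L (Day 7L + 1):

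- first follow-up diary window: Days 7L + 43 to 7L + 56
- second follow-up diary window: Days 7L + 99 to 7L + 112
- last follow-up visit: Day 7L + 113, which is on or after Day 169 when L ≥ 8

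So last-dose weeks 8 to 22, 15 in all, leave a subject in follow-up at Week 24. The gap from last dose to ET Visit is not in the documents; 7 days is assumed.

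| Last dose (week) | Diary days within 155–168 | Evaluable? |
|---|---|---|
| 8 (second window) | 14 | yes |
| 16 (first window) | 14 | yes |
| 9, 15, 17 | 7, all in one week | no |
| 21 (ET on Day 155) | 1 | no |
| 22 (ET on Day 162) | 8, split 7 + 1 | no (fewer than 3 in second week) |
| 10–14, 18–20 | 0 | no |

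Result: 2 of 15 evaluable, 13 of 15 not (87%).

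**3. Sensitivity.**

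- ±7-day visit windows (Table 4), each falling as favourably as possible: Weeks 8, 9, 15, 16 and 17 become evaluable, so 5 of 15, and 10 of 15 still fail.
- Every ET gap from 0 to 14 days, visits timed from the last dose: 80–87% fail. The one gain is a last dose at Week 22 with the ET Visit on Day 164 or later (a gap of 9 to 13 days), which gives 3 of 15.
- The same gaps with visits timed from the ET Visit (the exception above): 75–93% of those still in follow-up fail.

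**4. Week 48.** Week 48 is Day 337, so the endpoint uses Days 323–336. Adding 24 weeks throughout, follow-up reaches Week 48 for last doses at Weeks 32 to 46, and only Weeks 32 and 40 are evaluable.

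**5. How many subjects.** Section 9.3 plans on 20% dropout: 399 × 0.20 = 79.8. Assume last doses spread evenly over the 23 weeks 0–22, full agreement to follow-up and no rescue or prohibited medication:

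- still in follow-up at Week 24: 79.8 × 15/23 ≈ 52
- of these without an evaluable DD: 79.8 × 13/23 ≈ 45
- at 5% and 10% dropout: 399 × 0.05 × 13/23 ≈ 11 and 399 × 0.10 × 13/23 ≈ 23

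**6. Power.** With 212 and 106 subjects, SE = 4.76 × √(1/212 + 1/106) = 0.566 and 2.79/0.566 = 4.93, so power ≈ Φ(4.93 − 1.96) = 99.8%. The stated figure of at least 90% already allows for the 20% dropout.

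**7. Illustrative shift (assumption).** Suppose every active-arm leaver loses the whole 2.79-day effect but is imputed as if treated. The estimate then shifts by 0.14, 0.28 or 0.56 DD at 5%, 10% or 20% missing. The part due to leavers of step 5 is 13/23 of that, about 0.08, 0.16 or 0.32 DD. This is an extreme case and not a forecast.

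**The case against.** **The treatment-policy strategy is already served.** A reader might infer that the diary rule defeats the treatment-policy handling of treatment discontinuation. The documents do not support that. The Protocol Summary describes this intercurrent event (ICE 1) with subjects remaining in the study, and such subjects keep the daily diary. Table 7 does not repeat that limit, but the collection route exists all the same. This objection stands: the gap is missing data in study leavers only.

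**Many leavers cannot be reached.** Section 11.2 lists withdrawal, loss to follow-up and death among the reasons for leaving. The dead and the lost supply no diary, and those who withdraw may refuse. Users of rescue or relevant prohibited medication (ICE 2) receive the worst value whatever the diary shows. Exits clustered early would end follow-up before Week 24. All of this stands, so a reader should not take 45 as an expected count.

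**The follow-up diary may have another use.** One might infer that these windows feed no DD endpoint at all. That cannot be settled: parts of Tables 2 and 3 are redacted, analysis detail is deferred to the SAP, and the visits have a stated purpose of safety and clinical status.

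**The plan handles the missingness.** The tipping-point analysis tests the MAR assumption, and Section 11.2 urges sites to collect final data. Both are true. However, the first measures dependence on imputation without supplying a value, and the second does not tell a site or the eDiary to collect Weeks 22–24 or 46–48.

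**Conclusion.** The point holds as a gap in data collection for early study leavers. It is neither a contradiction nor an analysis error. The mechanism follows directly from the text. On schedule, and with a one-week ET gap, 13 of the 15 last-dose weeks that leave a subject in follow-up at Week 24 give no evaluable DD, and at least 10 of 15 still fail under the most favourable visit windows. Week 48 repeats this.

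The number of subjects cannot be derived. About 45 is an upper figure under 20% dropout, evenly spread exits, full agreement to follow-up and no ICE 2; 5–10% dropout gives at most about 11–23 under the same conditions. Actual exit timing is not documented and could move these figures either way. A loss of power might be inferred, but the planned power already absorbs the dropout. The gain on offer is observed values in place of some MAR-imputed ones. This is a cheap improvement.

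**What to change.** In Sections 6.4.2.1 and 6.3.1, Table 4 footnote p and Table 5 footnote l, add wording such as: early leavers who agree to Safety Follow-up also complete the mDSD at least for the 14 days before planned Week 24 (Induction leavers) or planned Week 48 (Maintenance leavers), when that date falls within their follow-up. Add a reminder call just before Week 22 or Week 46 (Table 4 footnote o, Table 5 footnote k). In Sections 9.6.1.2 and 9.6.3, state that the result is used as the observed DD unless ICE 2 applies.

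On the step 2 schedule, this makes an observed value possible for all 15 last-dose weeks instead of 2. The cost is protocol wording, an eDiary setting and a reminder call. It needs no new visit or procedure, and subjects already need the handheld for the follow-up windows. The downside is up to 14 extra evening entries per subject, which some leavers will decline.
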